14.0 BIOSTATISTICS

For the primary objective of this study, we will employ a Simon two stage design. Currently, the FDG-PET/CT normalization rate for ICE alone is between 50-60% therefore for a new treatment regimen, we would consider a normalization rate of 40% unacceptable. The goal of this study is to replace an intense inpatient regimen with an effective, less toxic regimen without impacting efficacy. Thus, we will set the desirable FDG-PET/CT normalization rate at 60% for the new treatment regimen (i.e., SGN-35 with or without ICE) and we will use 40% as our null hypothesis in employing the Simon two stage design. In the first stage, we will enroll 18 relapsed or refractory Hodgkin lymphoma patients who meet the criteria in Section 6. If 7 or fewer patients achieve FDG-PET/CT normalization either after SGN-35 alone or after SGN-35 combined with ICE, no additional patients will be enrolled and the regimen will be considered not promising in this cohort of patients. If 8 or more patients are FDG-PET/CT negative either after SGN-35 alone or after SGN-35 with ICE, then an additional 28 patients will be enrolled for the second stage. Among the total 46 patients, If 23 or more patients achieve FDG-PET/CT normalization either after SGN-35 alone or after SGN-35 with ICE, this treatment regimen will be declared effective. This decision rule has both type I error (declaring the new treatment regimen promising while it is actually not) and type II error (declaring the new treatment regimen not promising while it actually is) rate as 0.10. The early stopping (i.e., stop after the first stage with 18 patients) probability is 0.56 when the FDG-PET/CT normalization rate is 40%, and is 0.06 when the FDG-PET/CT normalization rate is 60%. We expect it will take 2-3 years to enroll 46 patients.

Furthermore, additional stopping rules are in place if we observe an unacceptable amount of toxicity due to SGN-35 or an unacceptable rate of relapse following transplant in the SGN-35-only group among the first 18 patients. We have defined an unacceptable rate of toxicity as grade 3 or more neuropathy occurring in 5 of the first 18 patients enrolled. We have defined an unacceptable relapse rate as a 50% rate of relapse within 3 months of transplant among the SGN-35-only patients.

As an additional criterion, we require that at least 7 out of the total 46 patients (15%) achieve FDG-PET/CT normalization after SGN-35 to call this new regimen a success. The purpose of this criterion is to exclude the situation that all patients may fail SGN-35 (i.e., persistent PET abnormalities) and hence must receive ICE salvage therapy, yet accidentally pass the above two-stage design. The threshold 15% was chosen because the previous phase I data show that about 30% of patients may achieve CR with SGN-35, and thus we believe it would be clinically meaningful to require at least 15% of patients to achieve PET normalization after SGN-35 to call it a success.

For the secondary objectives, we will report the stratified FDG-PET/CT normalization rates as sample proportions with their confidence intervals. Overall response rate to SGN-35 alone will be reported similarly. Toxicities will be summarized and tabulated. PFS and OS (see

definition in Section 12) will be analyzed using standard survival tools such as Kaplan-Meier estimation, log-rank tests and/or Cox regression models to incorporate various factors (such as Δ SUVmax, CD68, FoxP3, TIA-1, serum cytokine, etc.) and assess their correlation with PFS and/or OS. Competing risks analysis will be conducted if competing risk(s) exists (such as death without progression). Lab results including CD34 cell yield following mobilization will be reported as summary statistics.

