1.0 PROTOCOL SUMMARY AND/OR SCHEMA

In this study, we plan to treat patients with 2 cycles of weekly brentuximab vedotin (SGN-35); patients who achieve FDG-PET/CT normalization will proceed directly to autologous stem cell transplant (ASCT) and avoid salvage treatment with ifosfamide, carboplatin, and etoposide (ICE). Patients with persistent FDG-PET/CT abnormalities will receive 2 cycles of augmented ICE chemotherapy followed by repeat FDG-PET/CT. We aim to evaluate the rate of FDG-PET/CT normalization following 2 cycles of weekly brentuximab vedotin with or without augmented ICE in transplant eligible patients with relapsed or refractory HL. This study will enroll 46 patients.

Expansion Cohort

We will expand this study to include 20 additional patients. The expansion would again enroll patients who fail their front-line therapy for HL; however they will receive 3 cycles of weekly BV followed by reassessment by FDG-PET. Those who score Deauville 2 or better will proceed to ASCT while all others will receive 2 cycles of augmented ICE prior to consideration for ASCT. We aim to evaluate the rate of FDG-PET/CT normalization following 3 cycles of weekly brentuximab vedotin with or without augmented ICE in transplant eligible patients with relapsed or refractory HL.

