Brentuximab vedotin (SGN-35)

Antibody-drug conjugates (ADCs), which consist of cytotoxic agents or toxins chemically conjugated to a monoclonal antibody, potentially represent an advantage over treatment with chemotherapy because they are designed to deliver the cytotoxic agent specifically to tumor cells thereby resulting in an improved safety profile.

Brentuximab vedotin (cAC10-vcMMAE [4]) is a novel ADC that binds to the cell-surface marker CD30. After binding to CD30-positive cells, brentuximab vedotin is internalized releasing free MMAE that leads to cell death. CD30 was originally identified on RS cells, the malignant cell in HL, and is now used as a diagnostic marker for the disease. Brentuximab vedotin induces growth inhibition of HL cell lines in vitro and inhibits disease progression in both disseminated and subcutaneous HL xenograft models in immunodeficient mice.

Two phase I studies (evaluating different treatment schedules) and a phase II study demonstrated high efficacy with acceptable toxicity for brentuximab vedotin in rel/ref HL. The first phase I study enrolled 45 patients (42 with HL, 2 with systemic ALCL, 1 with angioimmunoblastic T-cell lymphoma) treated at dose levels of 0.1 to 3.6 mg/kg administered intravenously every 3 weeks⁷. The most common adverse events were fatigue, pyrexia, diarrhea, nausea, neuropathy peripheral, and neutropenia. Dose related peripheral neuropathy and neutropenia were observed. Notable serious adverse events considered at least possibly related to treatment included anaphylaxis, myocardial infarction, and peripheral neuropathy. One patient treated with 3.6 mg/kg died of septic shock (no organism identified) and febrile neutropenia that were considered treatment related. The maximum tolerated dose of brentuximab vedotin was 1.8 mg/kg administered every 3 weeks. Evidence of objective responses in this study led to the phase II study with brentuximab vedotin 1.8 mg/kg q3week in relapsed or refractory HL⁸. This study enrolled 102 patients with relapsed and refractory HL following ASCT. The overall response rate was 75% and complete response rate 34%, establishing brentuximab vedotin as a highly effective therapy in rel/ref and heavily pre-treated HL.

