The second phase I study evaluated weekly administration of brentuximab vedotin (day 1, 8, and 15 of 28 day cycles)⁹. The study enrolled 44 patients, 86% with HL. The maximum tolerated dose was determined to be 1.2mg/kg and the dose limiting toxicities were diarrhea and hyperglycemia. The incidence of peripheral neuropathy seen with this dosing schedule

was similar to that seen with every 3 week dosing. About 50% of patients experienced peripheral neuropathy, mostly grade 1 or 2. Five patients experienced grade 3 peripheral neuropathy, 3 with motor neuropathies after 4-9 months of treatment with brentuximab vedotin. Thirteen CRs and 9 PRs were seen with an overall response rate of 56%. Most notable was that the majority of the complete responses were seen at the first restaging performed 8 weeks into treatment (following 2 cycles). The tolerability, efficacy, and early responses seen with this dosing schedule make this an attractive agent to test as a salvage therapy prior to ASCT in rel/ref HL.

Rationale for salvage therapy with brentuximab vedotin

Standard salvage regimens administered before ASCT, such as ICE or DHAP, are inpatient therapies, associated with significant hematologic toxicity, and risk of myelodysplastic syndrome and infertility. A therapy that is less toxic but can still achieve the same rate of response is desirable. In particular, avoiding ICE chemotherapy, but achieving a similar rate of chemosensitivity using less toxic therapy would be considered a success. Weekly brentuximab vedotin is an attractive regimen to test in this setting because it is associated with encouraging response rates, and complete responses are seen after only 8 weeks, which is desirable for a salvage therapy leading to ASCT. In this study, transplant-eligible patients with rel/ref HL will receive 2 cycles of weekly brentuximab vedotin. FDG-PET/CT will be performed following 2 cycles and patients with PET-normalization will proceed to transplant. Patients with persistent abnormalities on FDG-PET/CT will receive standard salvage treatment with 2 cycles of augmented ICE chemotherapy prior to proceeding to ASCT.

Rationale for expansion cohort in patients who fail front-line therapy with brentuximab vedotin

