14.0.1 EXPANSION COHORT: BIOSTATISTICS

This study would be an expansion of our current study and therefore the data will ultimately be analyzed along with the data from our current study in which patients are receiving 2 cycles of BV. The goal of this expansion study is to determine whether the rate of FDG-PET normalization is improved with 3 cycles of BV when compared to 2 cycles. So far, we have observed a 28% rate of FDG-PET normalization following 2 cycles of BV; however an additional 14 patients (44%) were "good responders" to 2 cycles of BV and likely had the potential to achieve FDG-PET normalization had they received an additional cycle of BV. Based upon this, we estimate that the rate of FDG-PET normalization following 3 cycles of BV will be around 50%.

Allowing for type I and type II error rates of 0.2, and assuming a FDG-PET normalization rate of 28% with 2 cycles of BV, the number of patients required to show an improvement in FDG-PET normalization rate to 50% is 20.

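### The 20-patient, 3-cycle expansion cohort has no cohort-level neuropathy limit; the only such limit covers the first 18 patients, all on the 2-cycle plan

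*Combined protocol and SAP*

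**What the plan says.** Section 14.0 adds safety rules to the Simon two-stage design: "Furthermore, additional stopping rules are in place if we observe an unacceptable amount of toxicity due to SGN-35", or an unacceptable relapse rate after transplant, among the first 18 patients. The toxicity rule is then given a number: "We have defined an unacceptable rate of toxicity as grade 3 or more neuropathy occurring in 5 of the first 18 patients enrolled". The companion rule concerns relapse, not toxicity: "We have defined an unacceptable relapse rate as a 50% rate of relapse within 3 months of transplant among the SGN-35-only patients". The section states no target rate, error rate or stopping probability for the neuropathy rule. Its plan for toxicity analysis is otherwise to summarize and tabulate.

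Section 1.0 introduces the expansion: "We will expand this study to include 20 additional patients". Section 14.0.1 describes its purpose in efficacy terms: "The goal of this expansion study is to determine whether the rate of FDG-PET normalization is improved with 3 cycles of BV", compared with 2 cycles. It gives a sample size for that comparison and says nothing about toxicity. The expansion's design, intervention, treatment and evaluation sections (4.1.1, 4.2.1, 9.0.1, 10.0.1) contain no cohort-level toxicity rule either.

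Several controls do apply to every patient, expansion included:
- the dose-modification table in Section 5.0, to which Section 9.0.1 refers, including its provisions for neuropathy;
- the exclusion of baseline neuropathy above grade 1 (Section 6.2);
- removal for unacceptable toxicity (Section 13.0);
- institutional monitoring committees, described in general terms (Section 16.2).

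**The concern.** The plan sets a cohort-level neuropathy limit for patients on the shorter course and none for those on the longer one, and it gives no reason for the difference. The rationale for the expansion in Section 3.0 rests on PET results from the 32 evaluable patients. It reports no neuropathy results from the 37 then accrued.

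At stake is whether accrual to the 3-cycle cohort would pause at a pre-set point if severe neuropathy proved frequent. As written, that would depend on unscripted judgement. The trial could then conclude that 3 cycles improves PET normalization without having held the longer course to the toxicity limit applied to the shorter one, although Section 14.0 gives lower toxicity as part of the trial's purpose.

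**Working it through.** **1. Who the rule covers.** The limit applies to the first 18 enrolled (Section 14.0). Section 3.0 reports 37 of 46 main-cohort patients accrued as of April 2013, when it proposes the expansion. Since 37 > 18, every patient under the rule was on the 2-cycle plan and none of the 20 expansion patients can be among them.

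**2. Planned exposure.** Sections 4.2 and 4.2.1 give 1.2 mg/kg on 3 days per cycle.
- Main cohort: 2 × 3 = 6 doses; 6 × 1.2 = 7.2 mg/kg.
- Expansion: 3 × 3 = 9 doses; 9 × 1.2 = 10.8 mg/kg.
- Ratio: 9/6 = 1.5.

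**3. Behaviour of the existing rule.** The plan gives no operating characteristics for it, so there is no figure to reproduce. The boundary is 5/18 = 27.8%. With true grade 3+ rate p, the trigger probability is

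P(X ≥ 5 | n = 18) = 1 − Σ(x = 0 to 4) C(18, x) p^x (1 − p)^(18 − x).

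The benchmark is 5/44 = 11.4%: five grade 3 cases among the 44 patients enrolled in the weekly phase I study (Section 3.0). Its use here is an assumption, because the documents give no grade 3+ rate at 3 cycles. The other rates are scenarios and have no source in the documents.

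| True grade 3+ rate | P(at least 5 of 18) | Current text, expansion |
|---|---|---|
| 11.4% (5/44) | 0.046 | no rule |
| 20% | 0.284 | no rule |
| 30% | 0.667 | no rule |
| 40% | 0.906 | no rule |

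**4. Effect of reporting lag.** These are probabilities of reaching the limit, not of sparing patients. Section 14.0 expects 46 patients in 2 to 3 years, which is 46/36 = 1.3 to 46/24 = 1.9 per month. The last expansion dose is on day 71 (Section 10.0.1), about 2.3 months. If that accrual pace holds and a case is counted only at the end of the course (both assumptions), about 3 to 4.5 more patients enrol before a case counts.

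Take a lag of 4. At least one of the 20 places stays unfilled only if the fifth case falls among the first 15 patients, because 15 + 4 = 19 < 20. So the probability is P(X ≥ 5 | n = 15): 0.16 at a true rate of 20% and 0.48 at 30%. The mean number of places spared is 0.6 and 2.1. Cases that appear earlier in the course would shorten the lag.

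**The case against.** The strongest reply is that expansion patients are not unprotected. Section 5.0 sets out dose modification and discontinuation for neuropathy, Section 13.0 allows removal, and Section 16.2 places phase I and II trials under a data and safety monitoring committee. This stands. A reader might infer from Section 14.0.1 that neuropathy in the expansion is unlimited in every sense, and the documents do not support that. The gap is narrower: these controls act on individuals or in general terms, and none sets a rate at which accrual pauses. The main cohort had the same controls, and the sponsor still added a cohort rule there.

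A reader might also infer that the protocol's own background shows neuropathy rising with the number of cycles. It does not. The sentence "Dose related peripheral neuropathy and neutropenia were observed" comes from the every-3-week study across dose levels from 0.1 to 3.6 mg/kg, and it does not concern cumulative exposure. The weekly study is no closer: "Five patients experienced grade 3 peripheral neuropathy, 3 with motor neuropathies after 4-9 months of treatment with brentuximab vedotin". The expansion course ends at about 2.3 months. So the documents show no grade 3+ signal at 3 cycles. They also give no 3-cycle rate at all, and that uncertainty is a reason to monitor.

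A third tempting reading treats the second stage as an equal gap, since after 18 patients "then an additional 28 patients will be enrolled for the second stage" with no further neuropathy rule. That is true of the text. However, at most 46 − 37 = 9 main-cohort places were open in April 2013, and tying a safety look to the first-stage size is a defensible design choice. A count assessed at patient 46 could not stop accrual to that cohort in any case.

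Finally, the documents never justify 5 of 18, so carrying it over does not make it right for 3 cycles. This also stands and limits the recommendation.

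**Conclusion.** The point holds for the expansion cohort. The only cohort-level toxicity limit covers 18 patients on the 2-cycle plan; the 20 patients on the 3-cycle plan, with 1.5 times the planned doses, have none, and the plan does not say why.

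The benefit of closing the gap is real but moderate. The existing limit is unlikely to trigger at the assumed benchmark rate and more likely than not to trigger at 30%. With a cohort of only 20 and a plausible lag, it would often come too late to spare many patients, though it would still force a documented review. The operating characteristics assume independent patients with a common rate, and the lag figures assume the accrual pace and counting time stated above. The conclusion that a cohort-level rule is missing rests on the text alone and does not depend on any of these assumptions.

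**What to change.** Reconcile Section 14.0.1 with Section 14.0. State that the existing accrual-monitoring limit, grade 3 or higher neuropathy in 5 of the first 18 patients, applies to the expansion cohort. Count it among 3-cycle patients only and do not pool them with the 2-cycle cohort. When the fifth case occurs, suspend accrual and consult the data and safety monitoring committee. The sponsor should confirm that this limit suits the 3-cycle exposure or, if no cohort-level limit is intended, say so and give the reason.

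Report the rule's operating characteristics beside it: trigger probability 0.05 at a true rate of 11.4%, 0.28 at 20% and 0.67 at 30%, with a note that reporting lag lowers the practical effect. No extension of the rule to the second stage is needed.

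The cost is protocol wording, since Section 16.0 already collects treatment toxicities. The downside is about a 5% chance of an unneeded pause if the true rate is the assumed 11.4%.

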2.0 OBJECTIVES AND SCIENTIFIC AIMS

Primary objectives

1. Determine the rate of FDG-PET/CT normalization following salvage therapy with brentuximab vedotin (SGN-35) alone or followed by augmented ICE chemotherapy

Secondary objectives

1. Rate of FDG-PET/CT normalization with respect to the presence of previously determined prognostic factors: extranodal disease, bulk \geq 5cm, relapse within previously radiated fields, relapse within 1 year of initial treatment, and presence of B symptoms at relapse
2. Determine overall response rate (CR and PR) rate to brentuximab vedotin alone
3. Toxicity from brentuximab vedotin alone and followed by augmented ICE chemotherapy
4. Evaluate progression free survival (PFS) and overall survival (OS) with this treatment program and their correlation with: Δ SUVmax, expression of CD68, FoxP3, and TIA-1 by immunohistochemistry, serum cytokine levels, and the clinical factors listed in secondary objective #1.
5. Determine number of CD34 cells collected following this treatment program.

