All patients enrolled on this study will be required to have biopsy proven relapsed or refractory HL. This gives us the opportunity to prospectively analyze several markers on the biopsy specimens by immunohistochemistry. Based upon the recent report of the prognostic significance of CD68 (a marker of tumor associated macrophages)¹⁰ on outcome in newly diagnosed HL, we will look at this marker in our relapsed/refractory population. In addition, immunohistochemical analysis of HL biopsy specimens have shown high expression of TIA-1 (markers of cytotoxic t cells) and low expression of FOXP3 (markers of regulatory T cells) to be associated with poor prognosis both following primary treatment¹¹ and in the relapsed/refractory setting¹². We aim to confirm these observations and evaluate differences following treatment failure by analyzing these markers in both initial biopsies and relapsed/refractory biopsies for each patient.

Δ SUVmax analysis

For the purpose of this study, FDG-PET/CT scans will be interpreted by visual analysis where areas with uptake greater than the mediastinal blood pool will be considered positive. Visual analysis of early interim FDG-PET/CT may not represent the most accurate method of interpretation. Evaluation of changes in FDG uptake over time, rather than assessment of findings at a single time point, has been proposed as an alternative assessment. Intensity of FDG uptake can be measured as standardized uptake value, SUV, usually measured as highest activity concentration per lesion, or SUVmax. Treatment induced changes in SUV over time are referred to as Δ SUVmax. In patients with previously untreated diffuse large B-cell lymphoma, it has been suggested that these changes in SUV from baseline to interim scan after 2 cycles of chemotherapy may be more accurate than visual assessment of a single scan¹³. These authors founds that a Δ SUVmax of -67.5% between FDG-PET/CT scans performed before and after 2 cycles of chemotherapy reduced the number of false positive results and improved the prognostic value of FDG-PET/CT compared to visual

analysis. We plan to explore Δ SUVmax between FDG-PET/CT scans performed before brentuximab vedotin, after two cycles of brentuximab vedotin and after augmented ICE (if given) as a predictor of outcome. This will be done by retrospective analysis of the data set. No Δ SUVmax will be defined a priori for determination of treatment strategy.

Serum cytokines

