*****cycle 1 only**
- Modified Total Neuropathy Score (mTNS) and European Organization for Research and Treatment of Cancer (EORTC) quality of life questionnaire for chemotherapy-induced peripheral neuropathy (CIPN-20): *****cycle 2 only**

Tests to be performed day 8 and 15 of each cycle of brentuximab vedotin

- History and physical exam
- CBC (may be drawn within 24 hours pre-treatment)

Tests to be performed at the completion of 2 cycles of brentuximab vedotin:

- FDG-PET/CT (1-7 days after the last dose of brentuximab vedotin, between days 44 and 50). All studies will be obtained on dedicated PET/CT cameras. Patients must fast for 6 hrs prior to PET imaging, but intake of water or other non-caloric beverages is encouraged. When the patient arrives at one of the nuclear medicine imaging sites, a fingerstick blood glucose measurement will be obtained; patient with blood glucose levels > 200mg/dl are ineligible. Approximately 12 mCi of 18F FDG will be injected intravenously. Following an approximately 60-80 min uptake time, CT and PET images will be obtained from skull base to upper thigh using standard clinical imaging protocols. For a given patient, all serial PET/CT scans will be obtained on the same camera model.
- CT chest, abdomen, pelvis (1-7 days after the last dose of brentuximab vedotin, between days 44 and 50)

Within 1 week of last dose of SGN-35 (+/- 4 days)

- Hemoglobin A1c
- Cytokine levels (one 8.5 mL SST speckled red top tube - IL-10, IL-6, IL-1, TNF α)
- Modified Total Neuropathy Score (mTNS) and European Organization for Research and Treatment of Cancer (EORTC) quality of life questionnaire for chemotherapy-induced peripheral neuropathy (CIPN-20)
- Bone marrow biopsy (if BM was involved before treatment and post-SGN-35 PET scan is negative)

Interventions while receiving brentuximab vedotin (SGN-35)

Treatment days

Test/treatment	Pretreatment	1	8	15	22	29	36	43	44-50
SGN-35		x	x	x		x	x	x	
History and Physical		x	x	x		x	x	x	
CBC	x	x*	x*	x*		x*	x*	x*	
Comprehensive Metabolic Panel	x	x				x			
ESR	x	x				x			
Uric acid	x								
Lactate dehydrogenase	x								
Creatinine clearance**	x								

Hemoglobin A1c	x								x
Serum β -HCG***	x								
Hep B, C, HIV	x								
Cytokines		x							x
Neuropathy Questionnaire	x					x			x
BM Bx	x								****
FDG-PET/CT and CT CAP	x								x
Echo or MUGA	x								
PFTs	x								

*may be drawn within 24 hours pre-treatment; ** if creatinine >1.5; ***premenopausal females; ****if previously positive

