The following applies to patients receiving augmented ICE:

- A CBC and basic metabolic panel will be obtained upon each admission for chemotherapy and a 12-hour urine collection for creatinine clearance will be obtained prior to receiving carboplatin. Other laboratory evaluations during admission for ICE chemotherapy may be performed at the discretion of the inpatient attending physician. When receiving ifosfamide, urine will be monitored for hematuria by urinalysis.

The following will be performed within 21 days following the completion of augmented ICE:

- CT scan of the chest, abdomen, and pelvis
- FDG-PET/CT scan
- Bone marrow biopsy (if BM was involved before treatment and post-ICE PET scan is negative)

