12.0 CRITERIA FOR THERAPEUTIC RESPONSE/OUTCOME ASSESSMENT

Criteria for interim FDG-PET/CT assessment

Patients enrolled in this study will receive salvage treatment with brentuximab vedotin and those who achieve FDG-PET/CT normalization will proceed directly to ASCT without receiving standard salvage chemotherapy such as ICE or DHAP. Because this treatment strategy represents, for some patients, a departure from standard practice, or de-escalation of treatment, stringent criteria are required to designate those most appropriate for avoiding ICE chemotherapy. A five-point scale for assessing response on interim FDG-PET/CT scans, referred to as the “London criteria”, was developed by international experts in Nuclear Medicine and Oncology for use in diffuse large B cell lymphoma and HL¹⁷ and validated for use as interim assessment in HL patients.¹⁸ The 5-point scale is displayed in the following table.

Score	FDG-PET/CT scan result
1	No uptake above background
2	Uptake \leq mediastinum
3	Uptake $>$ mediastinum but \leq liver
4	Uptake moderately more than liver uptake, at any site
5	Markedly increased uptake at any site or new sites of disease

The score on this scale used to define a normal or abnormal scan depends upon the particular clinical strategy planned. For example, when escalation of treatment is planned based upon FDG-PET/CT results, defining an abnormal FDG-PET/CT by a score of 4 or 5 is appropriate to avoid overtreating patients. Conversely, when de-escalation of treatment is planned based upon FDG-PET/CT results, defining a persistently abnormal FDG-PET/CT by a score of 3, 4, or 5 is appropriate in order to avoid undertreating patients.

For the purpose of this study, a score of 1 or 2 will be considered a “normal” FDG-PET/CT scan because de-escalation of treatment is anticipated. All scores (1 through 5) will be recorded for each FDG-PET/CT scan and scans will be reviewed by either [name] or [name].

Progression free survival (PFS) and overall survival (OS) will be calculated from the time of initiation of brentuximab vedotin.

The response criteria developed by the International Harmonization Project for response assessment in lymphoma will be used to define complete response, partial response, and progression of disease in this study¹⁹. The definitions for response are detailed in the table below.

Table 2. Response Definitions for Clinical Trials					
Response	Definition	Nodal Masses	Spleen, Liver	Bone Marrow	

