CR	Disappearance of all evidence of disease	(a) FDG-avid or PET positive prior to therapy; mass of any size permitted if PET negative (b) Variably FDG-avid or PET negative; regression to normal size on CT	Not palpable, nodules disappeared	Infiltrate cleared on repeat biopsy; if indeterminate by morphology, immunohistochemistry should be negative	
PR	Regression of measurable disease and no new sites	≥ 50% decrease in SPD of up to 6 largest dominant masses; no increase in size of other nodes (a) FDG-avid or PET positive prior to therapy; one or more PET positive at previously involved site (b) Variably FDG-avid or PET negative; regression on CT	≥ 50% decrease in SPD of nodules (for single nodule in greatest transverse diameter); no increase in size of liver or spleen	Irrelevant if positive prior to therapy; cell type should be specified	
SD	Failure to attain CR/PR or PD	(a) FDG-avid or PET positive prior to therapy; PET positive at prior sites of disease and no new sites on CT or PET (b) Variably FDG-avid or PET negative; no change in size of previous lesions on CT			
Relapsed disease or PD	Any new lesion or increase by ≥ 50% of previously involved sites from nadir	Appearance of a new lesion(s) > 1.5 cm in any axis, ≥ 50% increase in SPD of more than one node, or ≥ 50% increase in longest diameter of a previously identified node > 1 cm in short axis Lesions PET positive if FDG-avid lymphoma or PET positive prior to therapy	> 50% increase from nadir in the SPD of any previous lesions	New or recurrent involvement	

Abbreviations: CR, complete remission; FDG, [¹⁸F]fluorodeoxyglucose; PET, positron emission tomography; CT, computed tomography; PR, partial remission; SPD, sum of the product of the diameters; SD, stable disease; PD, progressive disease.

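### The plan relates ΔSUVmax to PFS without saying how to treat patients whose progression is called on the same restaging imaging (minor, cheap to fix)

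*Combined protocol and SAP*

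**What the plan says.** Secondary objective 4 (Section 2.0) is to "Evaluate progression free survival (PFS) and overall survival (OS) with this treatment program and their correlation with" ΔSUVmax, among other factors. Section 3.0 (Δ SUVmax analysis) describes a retrospective exploration of the change between the scans before brentuximab vedotin, "after two cycles of brentuximab vedotin and after augmented ICE (if given) as a predictor of outcome". Section 14.0 names Kaplan-Meier, log-rank and/or Cox methods to incorporate "SUVmax, CD68, FoxP3, TIA-1, serum cytokine, etc.) and assess their correlation with PFS and/or OS".

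Section 12.0 fixes the time origin: "Progression free survival (PFS) and overall survival (OS) will be calculated from the time of initiation of brentuximab vedotin". The same section's response table defines progression as "Any new lesion or increase by ≥ 50% of previously involved sites from nadir", and the top score of its five-point PET scale covers "Markedly increased uptake at any site or new sites of disease".

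Section 10.0 pairs PET/CT and CT at each restaging. After brentuximab vedotin, the CT entry reads "CT chest, abdomen, pelvis (1-7 days after the last dose of brentuximab vedotin, between days 44 and 50", and the PET/CT has the same window. After ICE, "The following will be performed within 21 days following the completion of augmented ICE" introduces both scans. Section 10.0.1 repeats the pairing for the expansion cohort, with days 72-78 in its schedule for the scan after brentuximab vedotin.

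Two other provisions come close. Section 13.0 removes patients who progress on treatment from study. Section 14.0 foresees competing-risks analysis, with death without progression as its example. Neither says who belongs in the ΔSUVmax analysis.

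**The concern.** One restaging visit can supply both the predictor and the outcome. A patient with a new lesion on the imaging after brentuximab vedotin has a ΔSUVmax from that visit and, by the PFS definition, an event on the same date. That event was not predicted by the scan, because it was seen on it. If such patients also tend to show a small fall in SUVmax, the poor-ΔSUVmax group collects events at the scan date even when ΔSUVmax carries no information about what happens afterwards.

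The aim in Section 3.0 is to learn whether ΔSUVmax predicts outcome. An apparent association with PFS could partly restate progression that was already visible. With few PFS events in a study of this size, two or three such patients can matter.

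**Working it through.** **1. Is there a rule?** The plan has no landmark, re-set origin, time-dependent covariate or exclusion for this analysis. Section 13.0 ends study participation for on-treatment progressors but does not define an analysis set. The plan states no figure for this analysis, so there is none to reproduce.

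**2. How many patients might be affected?** The interim table in Section 3.0 (rationale for the expansion cohort) covers 32 evaluable patients. Nine normalized and went to transplant, and the rest are said to have gone on to augmented ICE. That is compatible with 0 of 32 progressing on the scan. The one-sided 95% upper bound for 0 of 32 is 1 − 0.05^(1/32) = 0.089. Two patients scored 5, and their progression status is not stated. If both had progressed, the rate would be 2/32 = 6.25%. No rate is given for the post-ICE scan or the expansion cohort.

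**3. What could that do to a test?** A null simulation shows direction and possible size. All of these inputs are assumed unless marked otherwise:
- N = 46, the main-cohort size in Section 14.0; 3,000 trials per cell; two-sided 5% log-rank test of poor against good ΔSUVmax.
- Scan at days 44-50 (Section 10.0); exponential PFS after the scan, unrelated to ΔSUVmax; 24-month PFS 70%; follow-up 24-30 months.
- Share with poor ΔSUVmax 28% or 50%. The 28% is a proxy from the interim table: 32 − 9 excellent − 14 good = 9, and 9/32 = 28%.
- Full concordance puts every on-scan progressor in the poor group. Half concordance forces half of them there and lets the rest follow the background share.
- On-scan progression of 0, 3, 6 or 9%, that is 46 × 0.03 = 1.4, 46 × 0.06 = 2.8 and 46 × 0.09 = 4.1 expected patients.

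False-positive rate with PFS from first dose and on-scan progressors counted as events:

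| Poor ΔSUVmax | Concordance | 0% | 3% | 6% | 9% |
|---|---|---|---|---|---|
| 28% | full | 0.052 | 0.116 | 0.199 | 0.331 |
| 28% | half | 0.049 | 0.078 | 0.099 | 0.131 |
| 50% | full | 0.058 | 0.058 | 0.098 | 0.150 |
| 50% | half | 0.048 | 0.049 | 0.058 | 0.066 |

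Repeat runs of the first row gave 0.20-0.22 at 6% and 0.33-0.35 at 9%. Rounded, the ranges are about 5-12% at 3%, 6-20% at 6% and 7-35% at 9%.

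**4. What removes it?** Keeping the first-dose origin and leaving out on-scan progressors gives 0.043-0.058. A landmark at the scan gives 0.043-0.059. The two are equivalent here, so the inflation comes from the on-scan events and not from the time origin.

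**5. Sensitivity.**
- With no concordance there is no inflation.
- With 24-month PFS of 50% instead of 70% (28% poor, full concordance), the rate is about 0.18 at 6% and 0.26 at 9%. That is lower, but still well above nominal.
- For a post-ICE group of 46 × 23/32 ≈ 33 patients with an assumed 24-month PFS of 65%, the range is about 6-17% at 6% on-scan progression, against about 4-6% with the landmark.

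**The case against.** The strongest reply is that the only data in the documents point to no problem after brentuximab vedotin. Every non-normalizing patient is reported to have gone on to ICE, while Section 13.0 would have removed a progressor. The SUV change reported for score-5 patients is a fall of 13% to 63%. At zero on-scan progression the test is at its nominal level. This stands as a limit on size. It does not settle the matter: progression in Section 12.0 is judged by new lesions or growth and not by SUV, 5 of 37 accrued patients were not evaluable for unstated reasons, and nothing is reported for post-ICE or expansion scans.

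A second reply is that the methods list in Section 14.0 is open and the ΔSUVmax work is exploratory, so a landmark is not ruled out. That is right as far as it goes. The accurate statement is that handling is unspecified, not that the plan commits to a biased analysis. But the stated PFS definition makes an on-scan progression an event, and no text takes that patient out.

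A third reply is that the upper figures are worst cases. This also stands: they need 9% on-scan progression, the upper bound for zero events, together with full concordance. With half concordance and a 50% split, the rate at 9% is 0.066.

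A reader might also infer that patients who progress before the scan bias the result. The documents do not support that: such patients would normally have no ΔSUVmax for that scan and so drop out. Nor does the argument carry over to OS, since a progression called on the scan is not a death.

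**Conclusion.** The gap is real and minor. The plan relates ΔSUVmax after brentuximab vedotin and after ICE to PFS from the first dose, and does not specify how to handle patients whose progression is called on the imaging that yields ΔSUVmax. Counting them as events can move the association away from the null.

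How far is not known. If no patient progresses on a scan, there is no bias at that scan, and the interim data allow this after brentuximab vedotin. The false-positive rates in the table depend on the assumed PFS, the share with poor ΔSUVmax, the concordance and the on-scan progression rate, none of which the documents supply. They show that a few patients could matter, not that they will.

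It would be too strong to read the two score-5 patients as progressors, or to treat the first-dose origin as the fault. The documents do not state those patients' progression status, and exclusion with the origin unchanged removes the inflation. ΔSUVmax drives no treatment decision, and the primary endpoint, two-stage rule and sample size are untouched.

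**What to change.** Keep PFS and OS from the first dose for overall reporting and for baseline factors. For each analysis of ΔSUVmax against PFS, add a sentence that only patients alive and progression-free after that scan are included, which is equivalent to a landmark at the scan. Report how many patients progressed on or before each scan. Nothing more elaborate, such as time-dependent coding, is needed to remove the inflation.

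The cost is one or two sentences of analysis text and routine programming. The analysis set loses a few patients and events, and the result then speaks only to prognosis after the scan, leaving out the earliest failures. The reported count keeps those failures visible. If nobody progressed on a scan, the rule excludes no one.
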